7.2. Reporting of AEs

AEs will be collected starting from the first procedure required by the study up to three months after patient's disease progression. Safety evaluation after progression will include follow-up of symptomatic skeletal related events until reach 2 years from the last dose of study treatment.

All study patients who experience AEs will be closely monitored during this time. All AEs should be recorded in the CRF.

All signs, symptoms, and results of procedures with abnormal diagnoses that are clearly related should be grouped together and reported as a single diagnosis or disorder wherever possible. Any other event that does not fulfill this definition will also be reported separately.

Reporting of SAEs and reporting period

Reporting requirements will comply with all applicable local regulations regarding safety reporting.

All SAEs and AESIs defined in the protocol will be reported to the Sponsor within a period of 24 hours from the time the investigator or any other member of the site staff becomes aware of the event, as follows:

- Regardless of the study drug received by the patient and whether or not the investigator considers this event to be related or not to the study drug, all SAEs and AESIs (as defined in this protocol), will be reported to MedSIR immediately, no later than 24 hours after any member of the study site staff becomes aware of the event.
- All information regarding the SAE and AESI should be obtained and recorded in full using the SAE form and sent to MedSIR.
- Follow-up information, copies of test results, event outcome and the opinion of the investigator as to the relationship between the IMP and the SAE and AESI, accompanied by other applicable documentation when it is requested, will be sent along with the SAE form, if available on the day the event is reported or as soon as possible if it is not.
- The original SAE reporting form of the Sponsor should be kept on file with the documentation from the CRF at the study site(s).

All SAE forms will be sent by the investigator or investigator staff to the Sponsor by e-mail and fax as indicated below:

E-mail: [contact]

Fax: [name]

Follow-up of the SAEs and AESIs will continue until they resolve, a stable outcome is reached, patient is lost to follow-up, or the patient dies.

MedSIR will be responsible for ensuring that events are reported to the European Medicine Agency (EMA), competent authorities, within the stipulated period, as needed.

AESIs

The investigator must report any AESIs to the Sponsor immediately (i.e. within 24 hours of learning of its occurrence) regardless of their seriousness (see section 7.2). In this study, AESIs include:

- An agent is considered infectious when it is suspected that an infectious agent has been transmitted via medication, any organism, virus or infectious particle (e.g., the prion protein that causes transmission of transmissible spongiform encephalopathies), pathogenic or not. Transmission of an infectious agent may be suspected due to clinical symptoms or laboratory results which indicate the presence of infection in an individual exposed to a medicine. This term will only be applied when drug contamination is suspected and not to any infections supported by mechanism of drug action, e.g. immunosuppression.

- Potential drug-induced liver damage which meets the analytic criteria of Hy's Law. The following laboratory abnormalities are indicative of possible Hy's Law cases and should be reported as AESIs:
 - Any increase in AST and/or ALT > 3 times the ULN.
 - Simultaneous increase in total bilirubin > 2 times ULN (or clinical jaundice if total bilirubin measurements are not available), except for patients who have been diagnosed with Gilbert's syndrome. In the case of patients with Gilbert's syndrome, an increase in direct bilirubin > 2 times ULN should be used.

Non-compliance

Definition: Non-compliance with applicable laws or institutional policies that govern research on human subjects to follow-up on ethics committee (EC) decisions. Non-compliance may occur due to ignorance or a deliberate decision to ignore the law, institutional policies, or EC decisions.

Non-compliance should be reported to MedSIR, the principal investigator of the study site and, if necessary, to the EC immediately, within 24 hours.

Serious non-compliance

Definition: Non-compliance that materially increases the risk of serious harm to patients or other persons, or which materially compromises patient rights or well-being.

Serious non-compliance should be reported to MedSIR, the principal investigator of the study site and, if necessary, to the EC immediately, within 24 hours.

Expedited reporting to Health Authorities

To determine the reporting requirements in cases of a single AE, the Sponsor will assess the expectedness of these events using the radium-223 SmPC.

The Sponsor will compare the severity of each event and its cumulative frequency as reported in the study with the severity and frequency reported in the pertinent source document.

Reporting requirements are also based on the investigator's assessment of causality and seriousness, which may be updated by the Sponsor as needed.

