3.2. Study schedule

The design of this study is divided into three well-defined phases:

- **Screening phase**

During this phase, subject eligibility is determined, including the documentation of baseline characteristics. This phase of the study will begin once the informed consent is signed by the patient and the procedures to be performed are described in section 5.1 of the protocol.

- **Treatment phase:**

When a patient is identified and all the study screening criteria have been met, a baseline blood sample will be collected to perform CTCs the patient will be treated with radium-223 at a dose of 55 kBq (after 2015 NIST implementation) per kilogram body weight, given at four-week intervals for six intravenous (IV) injections.

Patients will receive study treatment according to the protocol and will be prematurely discontinued if one of the following situations arises:

- Disease progression is confirmed radiologically and unequivocally. An event for progression will be determined by The Prostate Cancer Clinical Trials Working Group (PCWG2) modified criteria defined as the time from inclusion to the first event in clinical, radiological, or biochemical progression, or death as[21]:

- Bone metastases: The appearance of \geq two new lesions, and, for the first reassessment only, a confirmatory scan performed six or more weeks later that shows a minimum of two or more additional new lesions. The date of progression is the date of the first scan showing the changes.

- Soft-tissue lesions: Assesed according to the Response Evaluation Criteria in Solid Tumors (RECIST criteria) version 1.1.[22].

- Symptoms: Consider independently of other outcome measures. Document pain/analgesia at entry and measure repeatedly at three- to four-week intervals. Ignore early changes (\leq 12 weeks) in pain or health-related quality of life (HRQOL) in the absence of compelling evidence of disease progression. Confirm progression of pain or HRQOL endpoints \geq three weeks later.

- Clinical deterioration: Consider independently of other outcome measures. A deteriorating patient is one who moves from one clinical state to a worse clinical state which increases their individual risk of morbidity, including organ dysfunction, protracted hospital stay, disability, or death.[23].

- AEs which, according to the protocol or in the opinion of the investigator, can cause serious or permanent damage or which rule out further treatment with the study drug.

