3.6. Duration of post-treatment follow-up period (follow-up phase)

The efficacy follow-up period is defined as the time relapsed between the last treatment administration and disease progression, death, withdrawal of consent, or 34 months after the first patient has been included, whichever occurs first. Safety follow-up period is defined as 2 years since the last treatment administration.

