3.7. EoS

The EoS is defined as the Last Patient LastVisit (LPLV) at the end of the safety follow-up period (24 months after last dose of treatment). This is the last timepoint for data collection.

The last visit for efficacy evaluation will be take place within three following months after last patient's disease progression, death, withdrawal of consent or 34 months after the first patient has been included, whichever occurs first.

The last visit for safety and overall survival evaluation will be take place 2 years after last dose of study treatment of last patient. We include a 2-years extension after the end of the treatment to evaluate symptomatic skeletal related events. Additionally, analysis of overall survival will be also extended. Contact by telephone is permitted.

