A complete physical examination should include an examination of head, eyes, ears, nose, and throat as well as cardiovascular, dermatological, musculoskeletal, respiratory, digestive, genitourinary, and neurological systems. Changes to abnormalities identified during the baseline period should be recorded at all subsequent physical examinations. New or worsening abnormalities should be recorded as AEs, if applicable.

Physical exams should also include, as part of tumor assessment, evaluation of presence and degree of increase of lymph nodes, hepatomegaly, and splenomegaly. Limited physical exams will focus on symptoms.

Response and tumor assessments:

Tumor response will be assessed for all patients, unless they withdraw from the study for any reason not attributable to disease progression confirmed radiologically or clinically and who have not received an acceptable complete assessment of the disease. The non-measurable disease should be documented at screening and be re-assessed at every tumor assessment thereafter.

The initial assessment of tumor response will be performed at the end of cycle three. Subsequently, an efficacy follow-up will be carried out for all patients every 12 weeks ± 7 working days during the study until disease progression, the patient withdraws their consent, or death, whichever comes first. In this study, response and disease progression will be assessed using the PCWG2 guidelines for bone disease and the RECIST criteria version 1.1 for soft-tissue disease. Radiographic disease progression in bone will require persistence of new lesions on a confirmatory bone scan performed at least six weeks later. Soft-tissue progression will not require a confirmatory scan for purposes of analysis (Appendix 2: Response Evaluation Criteria in Solid Tumors Guidelines (RECIST criteria) version 1.1).

A torax, abdomen, and pelvis CT scan or MRI, and a bone scan must be performed at screening (no more than 28 days before the first trial treatment). Tumor assessments should include an assessment of all known and/or suspected sites of the disease wherever possible. Patients should have a series of selected lesions that can be assessed at each tumor assessment. The same radiographic procedure employed at screening should be used throughout the study (e.g., the use of the same contrast protocol for CT scans).

Laboratory assessments:

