6.9. Medication errors and overdose

Medication errors in this study may arise when the drug is administered at the wrong time or when the wrong dose strength is taken. Patient medication errors should be recorded in the relevant section in the CRF. In the event of an error in the administration of the medication, the Sponsor should be informed immediately.

Medication errors must be reported irrespective of the presence of an associated AE/SAE, including:

- Medication errors involving patient exposure to the IMP.
- Any possible medication errors or use of the medication not defined in the protocol which implicate the participating patient or not.

Regardless of whether the medication error is accompanied by an AE or not, in the judgment of the investigator, the medication error should be recorded in the AE page.

6.10. ***Treatment compliance***

Patients will receive treatment under the supervision of a physician licensed in the administration of radioisotopes. Personnel will check the administration volume and total radioactivity injected. The activity/dose (total and per body kilogram) will be recorded in the source data and the appropriate CRF.

6.11. ***Dose adjustments***

Every effort will be made to administer the full dosing regimen of radium-223. Adjustment of dose level is not permitted. Study visits during the treatment period should occur at four weeks intervals (within a window \pm 7 working days).

Dosing delays may be instituted under the following situations:

- Disease progression:

In this patient population, disease progression is expected. Bone pain is a prominent symptom; other symptoms may include fatigue, nausea, anorexia, depression, constipation (also secondary to opioids), bowel and bladder symptoms, lymphedema, neurological, and hematological complication as well as metastases to other organs, such as liver and lung. The investigator should delay cytotoxic chemotherapy, other systemic radioisotope, radiotherapy, or other investigational drug until the follow-up period. If such treatments have to be given during the treatment period, further study drug administrations must be discontinued. Patients with disease progression may continue treatment at the Investigator's discretion.

- Myelosuppression:

Treatment-related changes in hematology parameters may occur:

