 - 4. ECOG performance status will be assessed before trial drug administration and before the administration of each cycle.
 - 5. Relevant concomitant medication will be recorded at screening and on an ongoing basis.
 - 6. FACT-P, Version 04
 - 7. All AEs occurring during the trial and until the treatment discontinuation visit (end of study visit) have to be recorded with grading according to NCI-CTCAE version 4.0.
 - 8. Baseline assessments of the thorax, abdomen, and pelvis (preferably CT or MRI in case of contrast allergy) must be performed no more than 28 days before the first trial treatment. Baseline bone scan must be performed no more than 28 days before the first trial treatment. Post-baseline assessments have to be performed every 12 weeks \pm 7 working days after the first dose using the same imaging method and where possible obtained at the same institution for an individual patient as used during screening until progression disease. Radiographic bone progression will require the persistence of new lesions on a confirmatory scan at least six weeks later. In those patients who receive 6 treatment cycles, the radiological tumour assessment corresponding to week 24 will be performed for the EOT visit.
 - 9. Hematological test will be performed as per local standard of care and clinical indication before treatment administration. These values should be included: hemoglobin, hematocrit, red blood cell count, platelet count, and white blood cell count with differential count (neutrophils, lymphocytes, monocytes, eosinophils, and basophils).
 - 10. Biochemistry test will be performed as per local standard of care and clinical indication before first treatment administration and first day of follow-up. These values should be included: coagulation, chemistry with renal function analysis (serum creatinine, creatinine clearance according to the Cockcroft-Gault formula), liver function (AST, ALT, ALP, direct and total bilirubin), glucose, sodium, potassium, calcium, chloride, magnesium, uric acid, total protein, albumin, and lactate dehydrogenase.
 - 11. Blood sample for central laboratory prior to the start of study treatment, at the end of treatment and at time to documented progression disease (if the patient ends treatment due to progressive disease, only one blood sample will be sent at this point).

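### AE collection ends three months after progression with no minimum after the last injection, so a patient who progresses at week 12 but receives dose 5 or 6 has only 9 or 5 weeks of it

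*Protocol*

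**What the plan says.** Protocol 7.2 states: "AEs will be collected starting from the first procedure required by the study up to three months after patient's disease progression". It then continues symptomatic skeletal events to two years from the last dose.

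Three provisions bear on whether doses can follow the progression date:
- Section 3.2 dates bone progression to the first scan: "The date of progression is the date of the first scan showing the changes". Its stop rule is "Disease progression is confirmed radiologically and unequivocally".
- Section 5.2 adds: "Radiographic disease progression in bone will require persistence of new lesions on a confirmatory bone scan performed at least six weeks later".
- Section 6.11 allows more: "Patients with disease progression may continue treatment at the Investigator's discretion".

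Other texts give different end dates:
- The Appendix 1 grid marks AE reporting in every column, including EoS (Safety FUP). Note 7 to that row says: "All AEs occurring during the trial and until the treatment discontinuation visit (end of study visit) have to be recorded".
- Note 13 lists only skeletal events, survival and later therapy for the visits after progression.
- Protocol 3.6 says: "Safety follow-up period is defined as 2 years since the last treatment administration". Protocol 3.7 places the end of study "at the end of the safety follow-up period (24 months after last dose of treatment".
- The deviation table in SAP 6.1 expects the end-of-study visit within three months after progression.
- SAP 8.4.3 analyses events to three months after 'study discontinuation' and cuts non-fatal AEs at new anti-cancer treatment if that comes first. The SAP does not define the term. Protocol 5.5 uses it as a heading for withdrawal of consent and loss to follow-up.

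**The concern.** An AE window is normally tied to exposure. Here it is tied to a disease event that can come before the last exposure. Each week of dosing after the progression date takes one week off the AE follow-up that comes after the last dose, so the patients dosed longest after progression are observed for the shortest time afterwards. This does not need a departure from the stop rule: a site waiting for the confirmatory bone scan may properly give injections that later turn out to fall on or after the progression date.

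Safety is a listed secondary objective. Sites working from 7.2 and sites working from note 7 could also stop collecting at different times, and the SAP window matches neither text clearly.

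**Working it through.** The documents state no weeks-after-last-dose figure, so there is none to reproduce. The check is date arithmetic on nominal dates, ignoring visit windows.

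**Inputs**
- Injections at weeks 0, 4, 8, 12, 16 and 20 (Protocol 6.1).
- First post-baseline scan at week 12, before injection 4 (Protocol 5.2, Appendix 1 note 8).
- Confirmation at least six weeks later, so week 12 + 6 = 18 at the earliest. By then injections 4 and 5 may have been given.
- Three months taken as 13 weeks.

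**Formula.** With progression in week P and the last dose in week L, AE follow-up after the last dose is (P + 13) − L. It is below 13 weeks whenever L > P, and the shortfall is L − P.

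**Bone progression on the week-12 scan**

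| Last dose | Clock from first scan (closes 12 + 13 = 25) | Short of 13 weeks by | Clock from week-18 confirmation (closes 18 + 13 = 31) |
|---|---|---|---|
| Week 8 | 25 − 8 = 17 | 0 | 31 − 8 = 23 |
| Week 12 | 25 − 12 = 13 | 0 | 31 − 12 = 19 |
| Week 16 | 25 − 16 = 9 | 4 | 31 − 16 = 15 |
| Week 20 | 25 − 20 = 5 | 8 | 31 − 20 = 11 |

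Section 3.2 supports the first-scan column. Section 7.2 does not repeat the dating rule, so the last column is shown as a sensitivity; there only the six-dose patient falls short, by 13 − 11 = 2 weeks.

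**Other sensitivities**
- Three months as 12 weeks: 8 and 4 weeks instead of 9 and 5.
- One permitted four-week delay, dose 6 at week 24: 25 − 24 = 1 week. Two delays, dose 6 at week 28: 25 − 28 = −3, so 7.2 read alone closes before the dose.
- Progression at week 24 after six on-time doses: 24 + 13 − 20 = 17 weeks, no shortfall.

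**Note 7 for a patient with six on-time doses.** The end-of-treatment visit is at about week 24 (Appendix 1 note 8). The end of study under Protocol 3.7 is 20 + 104 = week 124. The SAP 6.1 timing, within three months after a week-12 progression, gives about week 25. One phrase in note 7 can therefore point to three different dates.

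**New therapy.** Protocol 3.4 asks that disallowed therapy wait four weeks after the last dose if possible: 16 + 4 = week 20, or 20 + 4 = week 24. A patient who starts then has non-fatal AEs cut in the analysis before week 25 already.

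**The case against.** The best defence is that the protocol covers most of what matters elsewhere. Possibly related serious events are notifiable at any time after treatment (7.1). Events of grade 2 or higher are followed to recovery (5.3), and skeletal events for two years from the last dose (7.2). AE checks at each cycle (5.2) and at end of treatment within 28 days (5.3) keep collection open in practice to about four weeks after the last dose. The Appendix 1 grid schedules AE reporting at the EoS (Safety FUP) visit. Sections 3.2 and 5.5 tell sites to stop treatment at progression. No passage requires three months of AE collection after the last dose; that yardstick is taken from what 7.2 gives a patient who stops at progression. For patients who move quickly to new therapy, a longer window adds no analysed non-fatal AEs.

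Most of this stands, and it makes the point minor. It does not remove it. The 7.1 rule depends on the investigator suspecting a link. The 5.3 rule follows known events rather than looking for new ones. The EoS mark in the grid sits beside a note 13 that lists no general AEs. Sections 3.2 and 5.5 do not cancel the wait for bone confirmation or the discretion in 6.11.

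A reader might infer that patients who progress are in general under-observed, that related serious toxicity goes unreported, or that collection really ends before the last injection. The documents support none of these. The shortfall needs dosing after the progression date, the 7.1 rule covers suspected serious reactions, and the cycle and end-of-treatment checks prevent an early close in practice.

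**Conclusion.** The point holds as a minor one. Section 7.2 sets no minimum after the last injection. With bone progression at week 12, first-scan dating and on-schedule doses, AE follow-up after the last dose is 9 weeks if dose 5 is the last and 5 weeks if dose 6 is. These are 4 and 8 weeks short of three months. A patient whose last dose is dose 3 or 4 has 17 or 13 weeks and loses nothing. Dating from a week-18 confirmation raises the 9 and 5 to 15 and 11; dose delays lower them.

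The possible loss is new non-serious AEs and serious AEs not suspected to be related; for non-fatal AEs it affects the analysis only until new anti-cancer therapy starts. The number of patients is unknown. The primary analysis is not affected, since it counts events up to progression or death. Separately, 7.2, the Appendix 1 grid and notes 7 and 13, Protocol 3.7, SAP 6.1 and SAP 8.4.3 do not give one consistent end date. A reader might take note 7 as a certain gap of 124 − 24 = 100 weeks between sites. That is only one possible reading, because the SAP 6.1 timing would place the visit at about week 25.

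**What to change.** Use one window in Protocol 7.2, Appendix 1 note 7 and SAP 8.4.3: collect and analyse all AEs and serious AEs from the first study procedure to the later of three months after progression and three months after the last radium-223 injection. In the SAP this replaces the undefined 'study discontinuation'; keep treatment-emergence as it is, and keep the new-therapy cut-off for non-fatal AEs in the analysis. Delete the bracketed reference to the end of study visit from note 7. State that AE reporting in the EoS column at 24 months covers only skeletal events and possibly related serious AEs.

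Cost: wording in three places. After week-12 progression, collection closes at max(25, 16 + 13) = week 29 if dose 5 is last and at max(25, 20 + 13) = week 33 if dose 6 is last, so 4 or 8 weeks later than now and more with dose delays. This may need one extra phone contact. For last doses at week 8 or 12 the close stays at week 25.
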